10.1.2.4 Visit 4: Week 2 (± 3 days)

Before dosing, the following assessments will be performed as listed in the study flow chart, [Section 1.3.2](#), which should be done in the following order:

- BDI-II ([Appendix L](#))
- Review of concomitant medications
- Vital signs: systolic and diastolic blood pressure (mm Hg), heart rate (bpm), respiratory rate (breaths/minute), and temperature ($^{\circ}\text{C}$)
- Laboratory assessments (to be performed by the central laboratory):
 - Hematology: CBC, with differential and platelet count; coagulation profile: PT, PTT, and INR
 - Biochemistry: Sodium, potassium, chloride, calcium, ALT, AST, GGT, ALP, total and conjugated bilirubin, urea, serum creatinine, glucose, albumin, total proteins
- Urinalysis (dipstick) including glucose, protein, bilirubin, urobilinogen, pH, specific gravity, blood, ketones, nitrite, and leucocytes. Central urinalysis will be performed if any abnormality is observed in the urinalysis dipstick test.
- Review of current medical conditions, with AE/SAE reporting (if any)
- Blood sampling for biomarker analysis
- Blood sampling for PK analysis (1 hour before dosing [pre-dose]) PK sample)

Remind patient to return to the clinic for next visit, bring their diary and any remaining capsules.

Remind patient to not take the dose at home on the clinic visiting day, the IMP will be taken at clinic.

10.1.2.5 Visit 5: Week 4 (± 3 days)

Before dosing, the following assessments will be performed as listed in the study flow chart, [Section 1.3.2](#), which should be done in the following order:

- BDI-II ([Appendix L](#))
- Review of concomitant medications
- Visual acuity check, slit lamp examination, and fundoscopy without pupil dilation
- Vital signs (orthostatic): systolic and diastolic blood pressure (mm Hg), heart rate (bpm), respiratory rate (breaths/minute), and temperature ($^{\circ}\text{C}$)
- 12-lead ECG
- Review of current medical conditions, with AE/SAE reporting (if any)
- Blood sampling for biomarker analyses

- Dispense IMP

Remind patient to return to the clinic for next visit, bring their diary and any remaining capsules.

Remind patient to not take the dose at home on the clinic visiting day, the IMP will be taken at clinic.

10.1.2.6 Visit 6: Week 13 (± 3 days)

Before dosing, the following assessments will be performed as listed in the study flow chart, [Section 1.3.2](#), which should be done in the following order:

- Whenever possible, the following scales and questionnaires should be done prior to clinical interaction with the Investigator:
 - BDI-II ([Appendix L](#))
 - PGIC ([Appendix N](#))
 - PDQ-39 ([Appendix O](#))
 - EQ-5D ([Appendix P](#))
 - HRPQ ([Appendix R](#))
 - FES ([Appendix Q](#))
- MDS-UPDRS, including H&Y ([Appendix F](#))
- PD-CRS ([Appendix G](#))
- Other questionnaires and scales
 - MoCA ([Appendix I](#))
 - Oral SDMT ([Appendix J](#))
 - TMT-A; TMT-B ([Appendix K](#))
- Review of concomitant medications
- General neurological examination
- Visual acuity check, slit lamp examination, and fundoscopy without pupil dilation
- Vital signs: systolic and diastolic blood pressure (mm Hg), heart rate (bpm), respiratory rate (breaths/minute), and temperature ($^{\circ}\text{C}$)
- Laboratory assessments (to be performed by the central laboratory):
 - Hematology: CBC, with differential and platelet count; coagulation profile: PT, PTT, and INR
 - Biochemistry: Sodium, potassium, chloride, calcium, ALT, AST, GGT, ALP, total and conjugated bilirubin, urea, serum creatinine, glucose, albumin, total proteins

- Urinalysis (dipstick) including glucose, protein, bilirubin, urobilinogen, pH, specific gravity, blood, ketones, nitrite, and leucocytes. Central urinalysis will be performed if any abnormality is observed in the urinalysis dipstick test.
- Urine pregnancy test (for WOCBP)
- Review of current medical conditions, with AE/SAE reporting (if any)
- Blood sampling for biomarker analysis
- Dispense IMP

Remind patient to return to the clinic for next visit, bring their diary and any remaining capsules.

Remind patient to not take the dose at home on the clinic visiting day, the IMP will be taken at clinic.

10.1.2.7 Visit 7: Week 26 (±3 days)

Before dosing, the following assessments will be performed as listed in the study flow chart, [Section 1.3.2](#), which should be done in the following order:

- Whenever possible, the following scales and questionnaires should be done prior to clinical interaction with the Investigator:
 - BDI-II ([Appendix L](#))
 - PGIC ([Appendix N](#))
 - PDQ-39 ([Appendix O](#))
 - EQ-5D ([Appendix P](#))
 - HRPQ ([Appendix R](#))
 - FES ([Appendix Q](#))
- MDS-UPDRS, including H&Y ([Appendix F](#))
- PD-CRS ([Appendix G](#))
- Other questionnaires and scales
 - MoCA ([Appendix I](#))
 - Oral SDMT ([Appendix J](#))
 - TMT-A; TMT-B ([Appendix K](#))
- Review concomitant medications
- Physical examination
- General neurological examination
- Visual acuity check, slit lamp examination, and funduscopy without pupil dilation

- Vital signs: systolic and diastolic blood pressure (mm Hg), heart rate (bpm), respiratory rate (breaths/minute), and temperature (°C)
- 12-lead ECG
- Laboratory assessments (to be performed by the central laboratory):
 - Hematology: CBC, with differential and platelet count; coagulation profile: PT, PTT, and INR
 - Biochemistry: Sodium, potassium, chloride, calcium, ALT, AST, GGT, ALP, total and conjugated bilirubin, urea, serum creatinine, glucose, albumin, total proteins
- Urinalysis (dipstick) including glucose, protein, bilirubin, urobilinogen, pH, specific gravity, blood, ketones, nitrite, and leucocytes. Central urinalysis will be performed if any abnormality is observed in the urinalysis dipstick test.
- Urine pregnancy test (for WOCBP)
- Review of current medical conditions, with AE/SAE reporting (if any)
- Blood sampling for biomarker and PK analyses as listed in study flow chart [Section 1.4.2](#)
- Dispense IMP

Remind patient to return to the clinic for next visit, bring their diary and any remaining capsules.

Remind patient to not take the dose at home on the clinic visiting day, the IMP will be taken at clinic.

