4.2 RATIONALE

4.2.1 Study rationale

GZ/SAR402671 is a novel glucosylceramide synthase (GCS) inhibitor that decreases the synthesis of GL-1. In Phase 1 healthy volunteer studies, once daily (qd) oral administration of GZ/SAR402671 at free base doses ranging from 3.72 mg to 14.9 mg was shown to be safe and reduce plasma levels of GL-1 within 2 weeks in a dose-dependent manner. In these studies, GZ/SAR402671 was absorbed with a median time to reach maximum plasma concentration observed (t_{max}) of 2.00 to 3.00 hours and eliminated with a pooled geometric mean terminal elimination half-life ($t_{1/2z}$) of 31.3 hours on Day 14.

In vitro studies demonstrate that GZ/SAR402671 is a potent and selective inhibitor of murine and human GCS in biochemical and cell-based assays. In vivo pharmacology studies utilized plasma GL-1 lowering as a pharmacodynamic marker of GCS inhibition. In vivo activity was established in rodents and dogs with reductions in plasma (rodent and dog) and tissue (rodents only) GL-1 following oral administration of GZ/SAR402671. In both species, the effects of GZ/SAR402671 on plasma GL-1 were dose-dependent and correlated with plasma exposure of the compound. In rodents, GZ/SAR402671 has been shown to cross the blood brain barrier and reduce the synthesis of the major isoform of GL-1 in the central nervous system (CNS; ie, C18 GL-1). Exposure in CNS has also been confirmed in dogs where the cerebrospinal fluid (CSF) concentrations of GZ/SAR402671 following repeat oral dosing were approximately 2-fold greater than the unbound plasma concentration of drug.

To date, no large-scale studies have specifically addressed the relative benefits and risks of different treatments for GBA-associated PD. Thus, there is a medical need to address motor, cognitive, and/or neuropsychiatric manifestations in GBA-PD patients. Patients included in this study will be early-stage PD patients who are heterozygous carriers of a GBA mutation, aged 18 to 80 years.

A substrate reduction therapy (SRT) treatment approach for GD type 1 (GD1) was first demonstrated by miglustat (Zavesca®), which is a weak and nonspecific GCS inhibitor. Due to its

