7.2.3 Exclusion criteria related to current knowledge of GZ/SAR402671 IMP

- E 22. Liver enzymes (alanine aminotransferase [ALT]/aspartate aminotransferase [AST]) or total bilirubin >2 times the upper limit of normal (ULN) at the time of screening. Patients with Gilbert's disease are excluded only from Part 1 participation.
- E 23. Renal insufficiency as defined by creatinine >1.5 times ULN at the screening visit.

- E 24. The patient has a documented diagnosis, as per local regulations, of any of the following infections: hepatitis B, hepatitis C, human immunodeficiency virus 1 or 2.
- E 25. The patient has received strong or moderate inducers or inhibitors of CYP3A4 (see [Section 17 \[Appendix E\]](#)) within 30 days or 5 half-lives of these medications, prior to randomization, whichever is longer.
- E 26. Use of the following medications within 5-elimination half-lives prior to the DAT neuroimaging evaluation: amoxapine, amphetamine, benztropine, bupropion, buspirone, cocaine, mazindol, methamphetamine, methylphenidate, norepinephrine, phentermine, phenylpropanolamine, selegiline, sertraline, citalopram, and paroxetine.
- E 27. The patient has, according to World Health Organization Grading, a cortical cataract > one-quarter of the lens circumference (Grade cortical cataract-2) or a posterior subcapsular cataract >2 mm (Grade posterior subcapsular cataract-2). Patients with nuclear cataracts will not be excluded.
- E 28. The patient is currently receiving potentially cataractogenic medications, including a chronic regimen (more frequently than every 2 weeks) of any dose or route of corticosteroids or any medication that may cause cataract or worsen the vision of patients with cataract (eg, glaucoma medications) according to the Prescribing Information.
- E 29. If female, pregnant (defined as positive beta-human chorionic gonadotropin [β -HCG] blood test) or lactating or breast-feeding.
- E 30. A marked baseline prolongation of QT/QTc interval on screening electrocardiogram (ECG) (such as a QTc interval >450 msec in male subjects and >470 msec in female subjects).

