9.3.3.7 Electrocardiogram (ECG)

Heart rate, ECG recordings, including time from ECG Q wave to the end of the s wave corresponding to ventricular depolarization (QRS interval), the time from the onset of the P wave to the start of the QRS complex (PR interval), QT interval, ECG ST-segment deviation (ST deviation), T-wave morphology, and U-wave presence or absence will be determined per local site procedure using automated and manual readings of all ECGs. All ECG recordings will be centrally read by independent experts. Refer to central ECG reading manual for more details.

Any clinically significant abnormality (eg, corrected QT or QTc >450 msec in males/ >470 msec in females) observed at the first screening visit (Day -60 to Day -1) upon Investigator review will be immediately rechecked for confirmation before making a determination regarding patient exclusion from the study. Additional ECGs may be performed if deemed clinically necessary by the Investigator (eg, diagnosis of AE) and will be documented in the eCRF.

In Part 1, a 12-lead ECG will be performed at screening, Day 1 (pre-dose and then 2, 4, and 6 hours postdose), and Week 4, and if applicable, at Week 28 and at the completion visit ([Section 1.3.1](#)).

In Part 2, an ECG will be performed at screening and Weeks 4, 26, 52, 104, 156, and 208 (See [Section 1.3.2](#) and [Section 1.3.3](#)).

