10.1.2.9 Visit 9: Week 52 (±14 days)

Visit 9 will be the last study visit of the blinded treatment period in Part 2.

Before dosing, the following assessments will be performed as listed in the study flow chart, [Section 1.3.2](#), which must be done in the following order:

- Whenever possible, the following scales and questionnaires should be done prior to clinical interaction with the Investigator:
 - BDI-II ([Appendix L](#))
 - PGIC ([Appendix N](#))
 - CGI ([Appendix M](#))
 - PDQ-39 ([Appendix O](#))
 - EQ-5D ([Appendix P](#))

- HRPQ ([Appendix R](#))
- FES ([Appendix Q](#))
- MDS-UPDRS, including H&Y ([Appendix F](#))
- PD-CRS ([Appendix G](#))
- Other questionnaires and scales
 - MoCA ([Appendix I](#))
 - Oral SDMT ([Appendix J](#))
 - TMT-A; TMT-B ([Appendix K](#))
- Review concomitant medications
- Physical examination
- General neurological examination
- Record of body weight measurement
- Vital signs (orthostatic): systolic and diastolic blood pressure (mm Hg), heart rate (bpm), respiratory rate (breaths/minute), and temperature (°C)
- 12-lead ECG
- Laboratory assessments (to be performed by the central laboratory):
 - Hematology: CBC, with differential and platelet count; coagulation profile: PT, PTT, and INR
 - Biochemistry: Sodium, potassium, chloride, calcium, ALT, AST, GGT, ALP, total and conjugated bilirubin, urea, serum creatinine, glucose, albumin, total proteins
- Urinalysis (dipstick) including glucose, protein, bilirubin, urobilinogen, pH, specific gravity, blood, ketones, nitrite, and leucocytes. Central urinalysis will be performed if any abnormality is observed in the urinalysis dipstick test.
- Urine pregnancy test (for WOCBP)
- Review of current medical conditions, with AE/SAE reporting (if any)
- Blood sampling for biomarker analyses, GCase activity and PK (as listed in study flow chart [Section 1.4.2](#))
- Pharmacogenetics DNA sample (optional; not applicable in Israel [[Appendix T](#)])
- Evaluate patients for eligibility (inclusion/exclusion criteria as listed in [Section 7.1](#), [Section 7.2](#), and [Section 10.1.2.10](#)) to transition to LTFU and receive GZ/SAR402671 treatment
- Full ophthalmology examination and photography (must be performed after the neurological examination)
- DAT scan

- Lumbar puncture for collection of CSF for PK (as listed in study flow chart [Section 1.4.2](#)) and biomarker analyses

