- Review of current medical conditions, with AE/SAE reporting (if any) (every 3 months [13 weeks] for Japanese patients only)
- Dispense IMP

At Visit 11/Week 104, Visit 13/Week 156, and Visit 15/Week 208 (ie, yearly), the following additional assessments will be performed, as listed in the study flow chart, [Section 1.3.3](#):

- Blood sampling for biomarker analysis
- Physical examination and record of body weight measurement
- 12-lead ECG
- Laboratory assessments (to be performed by the central laboratory):
 - Hematology: CBC, with differential and platelet count; coagulation profile: PT, PTT, and INR
 - Biochemistry: Sodium, potassium, chloride, calcium, ALT, AST, GGT, ALP, total and conjugated bilirubin, urea, serum creatinine, glucose, albumin, total proteins
- Urinalysis (dipstick) including glucose, protein, bilirubin, urobilinogen, pH, specific gravity, blood, ketones, nitrite, and leucocytes. Central urinalysis will be performed if any abnormality is observed in the urinalysis dipstick test.
- DAT scan
- Dispense IMP (except Visit 15/Week 208)
- Retrieve patient diary (at Visit 15/Week 208, only for patients who will transition to a long-term study with GZ/SAR402671).

Remind patient to return to the clinic for next visit.

Remind patient to not take the dose at home on the clinic visiting day, the IMP will be taken at clinic.

At Visit 15 (Week 208), patients will receive their last dose of GZ/SAR402671 at the clinic.

Visit 15 (Week 208) will be the last study visit for patients who will transition to a long-term study with GZ/SAR402671.

10.1.2.11 Eight-week follow-up visit (Period 4, end-of-study visit, Visit 16: Week 216 ±14 days)

This will be the last study visit. Patients who prematurely and permanently discontinue study medication should complete an end of treatment assessment visit (similar to Week 52/end of treatment visit for Period 2, Part 2) followed by a 8-week post-treatment follow-up visit (Visit 16). The following assessments will be performed as listed in the study flow chart, [Section 1.3.3](#), which should be done in the following order:

- BDI-II (Appendix L)
- MDS-UPDRS, including H&Y ([Appendix F](#))
- Review of concomitant medications
- Physical examination
- General neurological examination
- Visual acuity check, slit lamp examination, and fundoscopy without pupil dilation
- Vital signs: systolic and diastolic blood pressure (mm Hg), heart rate (bpm), respiratory rate (breaths/minute), and temperature (°C)

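### No scheduled ECG is specified at steady-state peak exposure: the Part 2 ECGs at Weeks 4, 26 and 52 are listed pre-dose and the later ones have no time relative to dose

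*Protocol*

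**What the plan says.** **Part 2, Weeks 4, 26 and 52.** Protocol Sections 10.1.2.5, 10.1.2.7 and 10.1.2.9 each open their list with "Before dosing, the following assessments will be performed as listed in the study flow chart", and the 12-lead ECG is an item in each list. At Week 52 the list is one "which must be done in the following order"; at Weeks 4 and 26 the order is only recommended. Patients do not dose at home on visit days: "Remind patient to not take the dose at home on the clinic visiting day, the IMP will be taken at clinic".

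**Part 2 overall.** Section 9.3.3.7 gives weeks but no clock times: "In Part 2, an ECG will be performed at screening and Weeks 4, 26, 52, 104, 156, and 208". In Section 10.1.2.10 the yearly Period 3 ECG is in a separate list of additional assessments that does not carry the pre-dose heading.

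**Part 1.** Section 9.3.3.7 schedules ECGs at "Day 1 (pre-dose and then 2, 4, and 6 hours postdose), and Week 4", then at Week 28 and the completion visit where applicable. Only Day 1, the first dose, has post-dose times. The completion visit is about 6 weeks after the last dose.

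**Pharmacokinetics.** Section 4.2.1 says that "GZ/SAR402671 was absorbed with a median time to reach maximum plasma concentration observed" of 2 to 3 hours, with a terminal half-life of 31.3 hours on Day 14. Dosing is once daily. Section 1.4.2 takes plasma 2 to 4 hours after dosing at Week 26 (P09) and Week 52 (P11). No ECG is tied to either sample.

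**The concern.** An on-treatment ECG is most informative about a concentration-related QTc effect when exposure is highest. With a half-life longer than the dosing interval, exposure builds up over repeated doses, so the highest exposure is a few hours after a dose at steady state. Neither set of timed ECGs covers it: the Part 2 ECGs at Weeks 4, 26 and 52 are at trough, and the timed Part 1 ECGs are at a peak that has not yet accumulated.

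Part 2 is also where this trial could best measure an effect, with about 108 patients per arm and concurrent placebo in Period 2. Section 11.4.3 turns these ECGs into on-treatment counts of potentially clinically significant abnormalities. A reader of those tables would not know that the Period 2 results describe trough exposure. In Part 1, the timed ECGs at the highest dose come from about 7 active patients (4 non-Japanese and 3 Japanese).

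**Working it through.** The plan gives no figure for this point, so there is none to reproduce. The check is a table of ECG times, then the size of the exposure gap.

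**1. Every scheduled ECG on or after the first dose**

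| ECG | Time relative to dose |
|---|---|
| Part 1 Day 1 | pre-dose, 2, 4, 6 h after the first dose |
| Part 1 Weeks 4 and 28 | not stated |
| Part 1 completion | about 6 weeks after the last dose |
| Part 2 Weeks 4, 26, 52 | pre-dose list |
| Part 2 Weeks 104, 156, 208 | not stated |

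None is required at steady-state peak. Some untimed ECGs may fall there by chance.

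**2. Inputs.** Half-life 31.3 h and tmax 2 to 3 h (Section 4.2.1); dosing interval 24 h (Section 8.1). Assumptions that the protocol does not state: linear one-compartment kinetics, the terminal half-life governing accumulation, and a QTc effect proportional to plasma concentration without delay.

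**3. Simple formulas**

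- k = ln 2 / 31.3 = 0.0221 per h.
- Accumulation = 1 / (1 − exp(−24k)) = 1 / (1 − 0.588) = 2.43.
- Trough/peak at steady state = exp(−k(24 − tmax)): exp(−22k) = 0.614 for tmax 2 h; exp(−21k) = 0.628 for tmax 3 h.
- First-dose peak/steady-state peak = 1 / 2.43 = 0.41.
- Steady-state trough/first-dose peak = 0.614 × 2.43 = 1.49.

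**4. With first-order absorption.** The absorption rate ka is solved from tmax = ln(ka/k)/(ka − k). The steady-state curve is proportional to exp(−kt)/(1 − exp(−24k)) − exp(−ka·t)/(1 − exp(−24ka)). The half-life range of 20 to 40 h is assumed, to show sensitivity.

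| Half-life | Accumulation | Steady-state trough/peak | First-dose peak/steady-state peak | Steady-state trough/first-dose peak |
|---|---|---|---|---|
| 20 h | 1.77 | 0.47–0.49 | 0.56 | 0.84–0.88 |
| 31.3 h | 2.43 | 0.62–0.63 | 0.41 | 1.50–1.55 |
| 40 h | 2.94 | 0.68–0.69 | 0.34 | 2.02–2.07 |

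Where a cell gives a range, it covers tmax 2 to 3 h. At 31.3 h a pre-dose ECG would show about 62% of the peak effect, a shortfall of about 38% (31% to 53% across the half-life range). The Day 1 ECGs in Part 1 would show about 41% (34% to 56%).

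**5. The existing PK window.** At 31.3 h the modelled steady-state peak comes at 1.6 to 2.4 h. Decline after the peak cannot be faster than exp(−kt), so with the earlier peak (1.62 h) the level at 4 h is at least exp(−0.0221 × (4 − 1.62)) = 0.95 of the peak. An ECG beside P09 or P11 is therefore close to peak.

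**The case against.** **The pre-dose heading may not be literal.** The Week 26 and 52 lists also contain PK samples taken 2 to 4 h after dosing, and at Week 52 the lumbar puncture. This is true, but for PK and CSF sampling the protocol points to Section 1.4.2 for times. The ECG has no such pointer. If the heading does not bind the ECG, its time is left to each site. Section 9.3.3.7 refers to a central ECG reading manual that is not shown.

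**No QT risk is documented.** Section 4.2.2 names no cardiac or QT signal, and Section 9.3.2 does not list ECG among the Part 2 safety endpoints. A reader might take E 30, placed among the criteria on current knowledge of the product, and the ban on QT-prolonging drugs as signs of a known risk. The documents do not support that: the same section holds hepatitis, HIV and pregnancy exclusions. A completed 14-day Phase 1 study also reached the 15 mg active dose. If it took ECGs at steady-state peak, trough monitoring here would be an ordinary choice. That cannot be seen, and this part of the objection stands.

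**The loss is moderate.** A reader might infer that an effect would go unseen. At 31.3 h the steady-state trough is about 1.5 times the first-dose peak, so the pre-dose ECGs attenuate an effect and do not hide it.

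**It may be late.** This amendment is dated February 2021, and Appendix U put the 52-week analysis in the first quarter of 2021. Many or all of the Week 26 and 52 ECGs may already have been taken.

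**Conclusion.** The point holds as a gap in measurement timing: no scheduled ECG is specified at steady-state peak exposure. Its consequence is conditional. If a concentration-related QTc effect exists, the pre-dose ECGs would show about 62% of the peak effect (47% to 69% for half-lives of 20 to 40 h) in the roughly 108 patients on active drug in Period 2. This rests on the kinetic and proportionality assumptions stated above.

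Two wider readings fail. The yearly Period 3 ECGs are untimed, so it is wrong to say that every Part 2 ECG is pre-dose. Nor do all 216 patients contribute trough-exposure data in Period 2, because half receive placebo. The documents contain no wrong figure or contradiction on this point. It is an inexpensive improvement to the safety data, not an error that undermines the trial.

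**What to change.** - In Sections 10.1.2.7 and 10.1.2.9, take the existing 12-lead ECG out of the pre-dose list and record it beside the 2 to 4 h PK sample (P09 at Week 26, P11 at Week 52), before the lumbar puncture at Week 52.
- In Section 9.3.3.7, state the time relative to dose for each Part 2 ECG, including Weeks 104, 156 and 208.
- Summarise QTc change against placebo at Weeks 26 and 52 together with the paired concentration.
- Report ECGs already taken pre-dose, and the Week 4 ECG, which has no PK sample beside it, as trough-exposure data.

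If the Week 26 and 52 visits are complete, what remains is to time the Period 3 ECGs and to label the earlier results. Period 3 has no concurrent placebo, so its ECGs cannot replace the randomised comparison.

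Cost: no extra visit or procedure, and no change to dosing or to any clinical rule. The screening ECG is not time-matched to a post-dose recording, so diurnal variation in the change from baseline is slightly larger, though expected to be equal in both arms. At Week 52 the ECG, plasma sample and lumbar puncture share one window and need sequencing.
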